8.5.2 SECONDARY ANALYSES

8.5.2.1 Efficacy

Phase 3 Segment

The secondary efficacy incidence endpoints will be analyzed in the same manner as the primary hypothesis, but without the hypothesis test p-value.

8.5.2.2 Immunogenicity

Phase 3 Segment

INO-4800	COVID19-311
Inovio Pharmaceuticals, Inc.	Clinical Protocol

Post-baseline increases from baseline in interferon-γ ELISpot response magnitudes will be compared between treatment groups using differences in medians and associated non-parametric 95% CIs.

Post-baseline increases from baseline in neutralizing antibody response titers will be compared between treatment groups using ratios of geometric mean fold-rises and associated t-distribution based 95% CIs.

The summaries listed above will be stratified according to disease status of the subjects and by baseline SARS-CoV-2 serostatus.

Valid samples for statistical analysis purposes will be those collected: at least 6 and no more than 30 days after Dose 2 for the Week 6 timepoint; at least 174 and no more than 198 days after Dose 2 for the Week 30 timepoint; and at least 356 and no more than 380 days after Dose 2 for the Week 56 timepoint. Baseline is defined as the last measurement prior to the first treatment administration.

The PP population will be used for these immunogenicity analyses.

8.5.3 SAFETY ANALYSES

8.5.3.1 Adverse Events

All AEs including injection-site reactions will be summarized among the Safety Population by frequency per treatment arm. These frequencies will be presented overall and separately by dose, and will depict overall, by system organ class and by preferred term, the percentage of subjects affected. Additional frequencies will be presented with respect to maximum severity and to strongest relationship to Study Treatment. Multiple occurrences of the same AE will be counted only once following a worst-case approach with respect to severity and relationship to Study Treatment. All serious AEs will also be summarized as above.

The main summary of safety data will be based on events occurring within 30 days of any dose. For this summary, the frequency of preferred term events will be compared between study arms with risk differences and 95% confidence intervals, using the method of Miettinen and Nurminen. As this analysis will use many event categories, and produce many confidence intervals, caution should be exercised when interpreting these confidence intervals. Separate summaries will be based on events occurring within 7 days of any dose and regardless of when they occurred.

The analyses listed above will be performed according to the Phase of the trial. For the Phase 2 segment, the analyses listed above will also be performed according to prior receipt of any non-study prophylactic COVID-19 vaccine. For the Phase 3 segment, the analyses listed above will also be performed according to SARS-CoV-2 serostatus at baseline.

For AE data, partial start dates will be imputed to the date of treatment to conservatively report the event as treatment-emergent, whenever the portion of the date is consistent with that of the study treatment. Otherwise, it will be imputed to the earliest date consistent with the partial date. A completely missing onset date will be imputed as the day of treatment. Partial stop dates will be assumed to be the latest possible day consistent with the partial date. AE duration will be calculated as (Stop Date – Start Date) + 1.

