In the Phase 3 segment, approximately 10,002 seronegative and 402 seropositive subjects 18 years of age and older will be randomized at a 2:1 ratio to receive either active investigational product (INO-4800, 2.0 mg) or placebo. See Table 2 and Figure 1. Approximately half of seronegative subjects and approximately half of seropositive subjects will be 18-50 years of age, and the other half will be \geq 51 years of age as is operationally feasible.

Subjects will be randomized in a stratified manner according to (a) age category (18-50 years vs. ≥51 years) on Day 0, and (b) presence or absence on Day 0 of any of the following underlying medical conditions that increase risk of severe COVID-19 disease, per U.S. Center for Disease Control (CDC) criteria [1], as listed below:

[figure not shown]
- Cancer
- Chronic kidney disease
- Chronic lung diseases, including Chronic obstructive pulmonary disease (COPD), asthma (moderate-to-severe), interstitial lung disease, cystic fibrosis, pulmonary hypertension
- Neurologic conditions including stroke or cerebrovascular disease that do not impact cognition
- Diabetes (type 1 or type 2)
- Hypertension
- Heart conditions, such as heart failure, coronary artery disease, or cardiomyopathies
- HIV infection
- Liver disease
- Obesity (BMI \ge 30 kg/m2)
- Sickle cell disease or thalassemia, or
- Smoking (current or former smoker).

Treatment Arm	Sero status	Expected Number of Subjects	Approx. Expected Number of Subjects by Age Group		Dosing Days	Number of Injections + EP per Dosing Visit	INO-4800 (mg) per injection	INO-4800 (mg) per Dosing Visit	Total Dose of INO-4800 (mg)		
		,	18-50	51+					(9)		
INO-4800	Seroneg	6668	3334	3334	0, 28	0.00	0.00	2	1.0	2.0	4.0
INO-4000	Seropos	268	134	134		.0 2	1.0	2.0	4.0		
Disasha	Seroneg	3334	1667	1667	0, 28	2	0	0	0		
Placebo	Seropos	134	67	67							
T . (.)	Seroneg	10002	5001	5001							
Total	Seropos	402	201	201							
Tot	al	10404		•							

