- n. Vital signs to be performed at COVID-19 assessment and convalescent visits include temperature, respiration rate, heart rate and oxygen saturation.
- o. Genotyping may also be performed on sample(s) collected at the COVID-19 assessment visit.
- p. Diaries to be used at selected sites only (estimated to include 711 subjects).
- q. Diary should be reviewed at the 14-day post-dose phone call or visit and collected at the next in-office visit.
- r. When possible, cellular and humoral immunology samples will be collected. Cellular samples will be collected at selected sites only.

INO-4800	COVID19-311
Inovio Pharmaceuticals, Inc.	Clinical Protocol

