3.4 SECONDARY ENDPOINTS

Table 7: Secondary Objectives and Associated Endpoints

Phase 2 Secondary Objectives	Phase 2 Secondary Endpoints
1. Evaluate the safety and tolerability of INO-4800 administered by ID	 Incidence of solicited and unsolicited injection site reactions
injection followed immediately by EP	1b. Incidence of solicited and unsolicited systemic adverse events (AEs) by system organ class (SOC), preferred term (PT), severity and relationship to investigational product
	1c. Incidence of serious adverse events (SAEs)
	1d. Incidence of adverse events of special interest (AESIs)
Phase 3 Secondary Objectives	Phase 3 Secondary Endpoints
1. Evaluate the safety and tolerability of INO-4800	1a. Incidence of solicited and unsolicited injection site reactions
	1b. Incidence of solicited and unsolicited systemic adverse events (AEs) by system organ class

	(SOC), preferred term (PT), severity and relationship to investigational product
	1c. Incidence of serious adverse events (SAEs)
	1d. Incidence of adverse events of special interest (AESIs)
	1e. Incidence of all-cause mortality
2. Evaluate efficacy of INO-4800 in the prevention of COVID-19 disease according to degrees of disease severity in subjects who are SARS- CoV-2 seronegative and RT-PCR negative at baseline	 2a. Incidence of non-severe COVID-19 disease in subjects who are SARS-CoV-2 seronegative and RT-PCR negative at baseline starting 14 days after completion of the 2-dose regimen until EOS 2b. Incidence of COVID-19 disease in subjects who are SARS-CoV-2 seronegative and RT-PCR negative at baseline starting 14 days after completion of the 2-dose regimen until EOS
	2c. Incidence of deaths due to COVID- in subjects who are SARS-CoV-2 seronegative and RT- PCR negative at baseline starting 14 days after completion of the 2-dose regimen until EOS
3. Evaluate the cellular and humoral immune response to INO-4800	3a. Antigen-specific cellular immune response measured by IFN-gamma ELISpot
	3b. Neutralizing antibody response measured by a pseudovirus-based neutralization assay
4. Evaluate the efficacy of INO-4800 in the prevention of COVID-19 disease in subjects who are SARS- CoV-2 seropositive at baseline	 Incidence of virologically-confirmed COVID-19 disease starting 14 days after completion of the 2-dose regimen until 12 months post-dose 2 (End of Study (EOS)) in subjects who are SARS- CoV-2 seropositive at baseline

3.5 **EXPLORATORY OBJECTIVE**

See Table 8.

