3.8 SAFETY ASSESSMENT

Subjects will be followed for safety during the trial through scheduled clinic visits and phone calls. AEs, regardless of relationship to study drug, will be collected from the time of consent until 28 days post-dose 2 (i.e., Day 56). SAEs, MAAEs and AESIs will be collected from time of consent until EOS. SAEs, AESIs, and treatment-related AEs will be followed to resolution or stabilization. For the Phase 2 segment and at selected sites in the Phase 3 segment, solicited local and systemic AEs will be collected for 7 days following each dose using a participant diary.

Subjects will also be monitored for COVID-19 disease.

Please refer to the Schedule of Events (Table 3 and Table 4) for safety assessments to be performed.

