Urine samples will be tested by dipstick for glucose, protein, and hematuria at Screening (Phase 2 segment only) and at visits specified in the Schedule of Events (Tables 3 and 4). If abnormal (presence of protein, hematuria, or glucose \geq 1+), a microscopic examination should be performed.

INO-4800	COVID19-311
Inovio Pharmaceuticals, Inc.	Clinical Protocol

Serology:

HIV antibody or rapid test will be performed at Day 0 only.

Antibodies to SARS-CoV-2 will be measured at Screening in the clinic using a rapid test which detects Spike protein antibodies and at pre-dose Day 0 and subsequent visits via testing at a study-designated lab which detects antibodies to Nucleocapsid protein. Timepoints are specified in the Schedule of Events (Tables 3 and 4).

Pregnancy Testing:

Pregnancy testing will be performed on women of childbearing potential (WOCBP). All women will be assumed to be of childbearing potential unless they are:

- Women who are post-menopausal as defined by reported spontaneous amenorrhea for ≥ 12 months;
- Women who are surgically sterile or have a partner who is sterile (i.e., vasectomy in males or tubal ligation, absence of ovaries and/or uterus in females). In the case of a vasectomy, subjects should wait six (6) months post-vasectomy to be considered sterile.

Phase 2: For WOCBP, a serum pregnancy test will be obtained at Screening and a urine pregnancy test will be performed immediately prior to any dosing and at the subject's last visit.

Phase 3: For WOCBP, a urine pregnancy test will be obtained at Screening and will be performed immediately prior to any dosing.

A negative result for urine β -HCG (test must have a sensitivity of at least 25 mlU/mL) must be available prior to each administration of IP. If the β -HCG test is positive, indicating that the subject is pregnant prior to completing the specified dose regimen, then no further IP will be administered. Every attempt should be made to follow pregnant subjects for the remainder of the study and to determine the outcome of the pregnancy (see Section 7.12).

DIARY

Diaries will be implemented in the Phase 2 segment of the protocol and at selected sites (estimated to include 711 subjects) in the Phase 3 segment. Subjects will be provided a diary to record the following solicited local and systemic AEs:

- Oral temperature and time taken (each daily entry before 11:59 pm)
- Solicited systemic symptoms
- Solicited local injection site symptoms
- Concomitant medications

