8.4 ANALYTICAL POPULATIONS

Analysis populations will be:

The per-protocol (PP) population includes all subjects who receive all doses of Study Treatments and have no protocol violations. Subjects in the PP population will be grouped to treatment arms as randomized. Subjects excluded from the PP population will be identified and documented prior to unblinding of the trial database. Analyses on the PP population among those who are baseline SARS-CoV-2 seronegative and RT-PCR negative will be primary for the analyses of efficacy in the Phase 3 segment of this trial.

The modified intention to treat (mITT) population includes all subjects who receive at least one dose of Study Treatment. Subjects in this population will be grouped to treatment arms as randomized. Analysis of the mITT population will be considered supportive for the corresponding PP population for the analyses of efficacy in the Phase 3 segment of this trial.

The intention to treat (ITT) population includes all subjects who are randomized. Subjects in this sample will be grouped to treatment arms as randomized. Analysis of the ITT population will be considered supportive for the corresponding PP population for the analyses of efficacy in the Phase 3 segment of this trial.

The safety analysis population includes all subjects who receive at least one dose of Study Treatment. Subjects will be analyzed according to the treatments received.

8.5 **DESCRIPTION OF STATISTICAL METHODS**

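### Phase 3 solicited reactions are diary-collected in about 711 of 10,404 subjects but summarised over everyone dosed, which understates their incidence by an unknown amount

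*Protocol*

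**What the plan says.** References are to protocol version 7.0.

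- **Endpoints.** Table 7 (Section 3.4) lists Phase 3 secondary endpoint 1a as "Incidence of solicited and unsolicited injection site reactions". Endpoint 1b is the counterpart for systemic adverse events.
- **Collection.** Section 3.8 limits diary collection in Phase 3: "at selected sites in the Phase 3 segment, solicited local and systemic AEs will be collected for 7 days following each dose using a participant" (the quote stops just before the instrument is named). Section 6.4 (Diary) places diaries "at selected sites (estimated to include 711 subjects) in the Phase 3 segment", and Table 4 footnote p gives the same number. Under Section 6.4, diary entries of Grade 1 or higher are recorded as AEs unless they belong to ongoing medical history, so they feed the general AE tables.
- **Size.** The synopsis states that "approximately 10,002 seronegative and 402 seropositive subjects 18 years of age and older will be randomized at a 2:1 ratio".
- **Denominator.** Section 8.4: "The safety analysis population includes all subjects who receive at least one dose of Study Treatment".
- **Analysis.** Section 8.5.3.1: "All AEs including injection-site reactions will be summarized among the Safety Population by frequency per treatment arm". The main summary covers 30 days after any dose and has Miettinen-Nurminen risk differences. The same section adds: "Separate summaries will be based on events occurring within 7 days of any dose". The splits given for Phase 3 are by segment and baseline serostatus. Nothing separates diary from non-diary subjects, or solicited from unsolicited events.
- **Status.** Section 8.1 says that the formal statistical analysis plan is contained in Section 8. The denominator is therefore a stated rule and is not left to a later document.

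**The concern.** An incidence is interpretable when its numerator is sought in the same way across its denominator. Here a small group is prompted daily about named symptoms for a week after each dose, and everyone else is asked about events at visits and calls. A subject without a diary who had a mild reaction and did not report it counts as a subject without a reaction. At stake are the Phase 3 incidences of solicited reactions and their risk differences against placebo. These are descriptive secondary safety results. The primary efficacy test is not involved.

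**Working it through.** **Inputs**
- Phase 3 total: the Table 2 cells sum to 6,668 + 268 + 3,334 + 134 = 10,404, which reproduces the stated total. The arms are 6,936 and 3,468.
- Diary subset: 711, or about 474 and 237 at 2:1.
- Diary fraction: f = 711 / 10,404 = 0.068, so 1 − f = 0.932.
- Contact without a diary: observation for 30 minutes after dosing (Section 6.4.5), new AEs collected after each administration (6.1.2.1), and queries that include injection-site reactions at visits and calls (6.4.4). The first scheduled contact is Day 14 after dose 1 (6.1.2.2) and Day 42 after the Day 28 dose (6.1.2.3), about 14 days after each dose. The diary runs from the evening of dosing through 6 days post-dose.

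**Formula.** Let p be the rate under diary collection and c the share of those reactions captured without a diary. Assume that c, f and the underlying reaction rates do not depend on having a diary or on arm, except that p may differ by arm. Then

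pooled rate = f·p + (1 − f)·c·p = p × [0.068 + 0.932c].

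The bracket is common to both arms, so the risk difference shrinks by the same factor and the relative risk is unchanged.

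**Results.** The protocol gives neither p nor c. The 10% column is the lower limit of the protocol's very-common class (Table 5). The last column assumes diary rates of 40% and 20% in the two arms. Half-widths are simple Wald 95%, 1.96 × √[p₁(1−p₁)/n₁ + p₂(1−p₂)/n₂].

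| c | Factor | Diary rate 10% reads as | Diary difference of 20 points reads as (half-width) |
|---|---|---|---|
| 0 | 0.07 | 0.7% | 1.4 (0.5) |
| 0.25 | 0.30 | 3.0% | 6.0 (1.1) |
| 0.5 | 0.53 | 5.3% | 10.7 (1.4) |
| 0.75 | 0.77 | 7.7% | 15.3 (1.6) |
| 1 | 1.00 | 10.0% | 20.0 (1.8) |

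In the diary subset alone, the 20-point difference has half-width 1.96 × √(0.24/474 + 0.16/237) = 6.7 points. The pooled interval is narrower but is centred on a diluted value for any c below 1.

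**How firm is 711?** It is labelled an estimate. It equals 10.0% of the version 6.0 total (711 / 7,116) and may have been carried over. If the subset were instead 10% of 10,404, the factor would be 0.10 + 0.90c: 0.10, 0.33, 0.55 and 0.78 at c = 0, 0.25, 0.5 and 0.75. The conclusion does not change.

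**The case against.** The strongest reply is that reactions are actively sought in subjects without a diary. Everyone is watched for 30 minutes, new AEs are collected after each administration, injection-site reactions are named in the routine queries, subjects are told to report events immediately, and the injection-site grading scale is not confined to diary sites. This stands: c is above zero, and nothing in the protocol says that it is small.

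A reader might infer that the reported rates would be several-fold too low. That holds only when capture is low; at c = 0.5 the pooled rate is about half the diary rate, and at c = 0.75 about three quarters. A reader might also infer that a large excess over placebo would nearly vanish, for example 30 points from a 30% vaccine rate. That would require no reactions on placebo, yet placebo recipients also receive two intradermal injections with electroporation at each dosing visit (Section 5.2).

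Three further points are fair:
- Diary use depends on site, and allocation is randomised and blinded, so the dilution is not expected to favour either arm on the ratio scale.
- AE analyses are done by segment and no Phase 2 to Phase 3 comparison is planned. Phase 2 also has diaries in all subjects, about 150 of them on the 2.0 mg regimen.
- The full Safety Population is the right denominator for unsolicited AEs, SAEs, MAAEs and AESIs.

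These points limit the size and scope. They do not remove the mismatch for solicited reactions.

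**Conclusion.** The point holds for Phase 3 solicited reactions. Section 8.5.3.1 fixes a denominator of which about 93% has no diary, so the solicited parts of endpoints 1a and 1b, and their risk differences, are understated for any c below 1. The multiplier lies between 0.07 and 1, and the documents do not allow it to be narrowed. Even at c = 0.75, a reaction occurring in 10% under diary collection would be reported as 7.7%, one frequency class lower in the protocol's own Table 5.

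This rests on diary-site subjects having the same underlying reaction rates as the rest, and on equal capture without a diary in both arms. If capture differed by arm, for instance because more severe reactions are reported more readily, neither the common factor nor the preserved relative risk would hold exactly. The change should be made, but it concerns descriptive secondary safety tables and no hypothesis test.

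**What to change.** In Section 8.5.3.1, for Phase 3:

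- Define a solicited-safety subset: subjects at diary sites who received at least one dose and have any diary data.
- Summarise solicited local and systemic reactions within 7 days of each dose in that subset, using its size as the denominator, with between-arm risk differences and 95% confidence intervals.
- Tabulate these reactions separately from unsolicited AEs, SAEs, MAAEs and AESIs, which stay in the full Safety Population.

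The cost is a few sentences, one extra population flag and wider intervals (in the illustration above, a half-width of 6.7 points). No additional data collection is needed.

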7.9 SAFETY DATA REPORTING PERIOD, METHOD OF COLLECTION AND SUBMISSION

All AEs will be collected from the time informed consent is obtained through Day 56. MAAEs, AESIs and SAEs only will continue to be collected after the Day 56 visit and will be followed to resolution or stabilization. This information will be captured in the CRF.

If the Investigator determines that the AE meets serious criteria, then the AE will be recorded as an SAE.

SAEs and AESIs will be reported to the Sponsor from the time the subject signs the informed consent until the last visit.

All SAEs (regardless of causal relationship) and AESIs will be reported on the SAE CRF Form and submitted to the Sponsor via EDC within 24 hours of becoming aware of the event. In the event the EDC is unavailable, the SAE/AESI Report Form (paper) should be used and submitted to the Sponsor within 24 hours of becoming aware of the event. In that case, the SAE Report Form will be either emailed to [contact] or faxed to the sponsor within SAE Report Form must be kept at the clinical trial site.

The event will be data entered into the CRF.

[figure not shown]
For the events that are considered an AESI, the Investigator will contact the Sponsor within 24 hours of becoming aware of the event to discuss whether dosing should continue.

Table 11: SAE Contact Information

Sponsor Safety Email: [contact]
Sponsor Safety Fax:
Sponsor Safety Phone:

Table 12: Medical Monitor Direct Contact Information

Primary point of contact, ICON Medical Monitor: , M.D.

All SAEs, treatment-related AEs, MAAEs and AESIs must be followed by the Investigator until resolution or return to baseline status, stabilization of the event (i.e., the expectation that it will remain chronic), even if it extends beyond the clinical trial reporting period or until it is determined that the subject is lost to follow up.

Follow-up information is to be submitted to the Sponsor on an SAE Report Form and within 24 hours of becoming aware of the information.

If medical records are submitted to the Sponsor with the SAE Report Form, the clinical trial site must:

- Redact the medical records of all personal data (e.g., confidential subject data, Personal Identifying Information [PII])
- Provide the subject's assigned identification number (SID) on the records

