8.5.8 MISSING VALUES

Missing data will not be imputed.

For the ITT analyses of efficacy in the Phase 3 segment, subjects with missing or unevaluable data regarding case definition will be considered cases (failures).

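### The AE onset imputation rule ignores a known stop date, so an event that ended before Dose 1 can be counted as treatment-emergent with a zero or negative duration

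*Protocol*

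**What the plan says.** Protocol version 7.0, Section 8.5.3.1, sets three rules for AE dates.

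- Partial onset: "partial start dates will be imputed to the date of treatment to conservatively report the event as treatment-emergent", on the single condition "whenever the portion of the date is consistent with that of the study treatment". If the known part does not fit, onset goes to the earliest date that the partial date allows.
- Wholly missing onset: "A completely missing onset date will be imputed as the day of treatment". No condition is attached.
- Stop date: "Partial stop dates will be assumed to be the latest possible day consistent with the partial date".

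Duration follows as "AE duration will be calculated as (Stop Date – Start Date) + 1".

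The same section builds its tables on time since dose: "The main summary of safety data will be based on events occurring within 30 days of any dose", with risk differences and 95% confidence intervals between arms. There is a further summary for the first 7 days and one that disregards timing.

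On collection, Section 7.9 says: "All AEs will be collected from the time informed consent is obtained through Day 56". Section 6.1.1 allows screening up to 30 days before Day 0 and collects AEs at that visit. Section 6.1.2.1 collects them again on Day 0 before the dose is given. Section 8.1 states that Section 8 is itself the formal statistical analysis plan.

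**The concern.** Moving an uncertain onset to the dosing day is a usual safety convention when the timing really is unknown. Here the rule applies even when the record shows that the event was over before the first dose. The stop date is handled in its own sentence and never limits the start.

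A pre-dose AE with an incomplete onset date can therefore appear in the safety tables as an event that began on the day of vaccination, although its own stop date rules that out. The 7-day summary and the main 30-day comparison both depend on time since dose, so both would contain events that the product could not have caused. The zero or negative duration is the visible sign that the imputed start contradicts the recorded stop.

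**Working it through.** **Inputs**

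- Onset rules, stop rule and duration formula: Protocol 8.5.3.1.
- AE collection from consent: 7.9. Pre-dose period of up to 30 days: 6.1.1.
- Assumptions: the treatment date is that of Dose 1, and the 7-day and 30-day windows run forward from the dose. The calendar dates below are illustrations chosen inside the collection period. The protocol gives no figure to reproduce on this point.

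**Can such a record exist?** Yes. AEs are recorded at Screening and again before dosing on Day 0, so an AE can begin and end before Dose 1.

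**Worked case.** Onset recorded as October 2021 with the day missing, stop on 4 October 2021, Dose 1 on 20 October 2021.

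1. The known part (month and year) fits the treatment date, so onset is imputed as 20 October, which is day 0.
2. Duration = Stop − Start + 1 = 4 − 20 + 1 = −15 days.
3. Day 0 lies in both windows, so the event is counted in both summaries. It ended 20 − 4 = 16 days before the dose.

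**General form.** If the stop date is s days before Dose 1 and onset is moved to day 0, then duration = (−s) − 0 + 1 = 1 − s. This is 0 for s = 1 and negative for s of 2 or more.

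| Onset as recorded | Stop day | Imputed onset | Duration | In 7- and 30-day summaries |
|---|---|---|---|---|
| Missing | −1 | 0 | 0 | Both |
| Missing (true onset day −20) | −10 | 0 | −9 | Both |
| Dosing month only (true onset day −23) | −19 | 0 | −18 | Both |
| Missing, edge of the screening period | −30 | 0 | −29 | Both |
| Missing (true onset day −6) | 0 | 0 | 1 | Both |

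None of these events began after the dose. The last row has an acceptable duration, so a stop-date check alone would not find it. It is found only by asking whether the AE was already on record before dosing. The same holds for an AE recorded before dosing that is still ongoing, or whose partial stop date is pushed past the dose by the latest-day rule.

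**With the correction.** In the worked case the stop date precedes Dose 1, so the event is pre-treatment and leaves both windows. If the plan's own fallback (the earliest date consistent with the partial date) is then used, onset is 1 October and duration is 4 − 1 + 1 = 4 days.

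**The case against.** The best defence is that the rule is openly conservative and does not depend on arm. Under blinding, misplaced events should arise at similar rates in both arms, so the risk differences gain noise and not a systematic shift. The summary that disregards timing is untouched by window membership, and no duration analysis is specified, so no stated result rests on the negative values. All of this stands and limits the importance of the point.

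The case is also uncommon. Illness that began before consent is not an AE (Section 7.2), screening lasts at most 30 days, and Screening and Day 0 may be one visit. A site that knows the stop to the day will often be able to date the start. That makes the error rare. It does not make the rule right, and Section 8.1 leaves no separate plan to which the missing condition could be deferred.

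A reader might infer three stronger points, and the documents do not carry them.

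- *That months-late events will flood the early windows.* On the literal text, a serious, medically attended or special-interest event with a wholly missing or year-only onset could be moved to day 0. With the month known, the shift is at most about 30 days. Phase 3 contacts are two-weekly to Day 210 and roughly monthly afterwards (6.1.2.4), and serious and special-interest events must be reported within 24 hours of awareness (7.9), so such dates should be unusual. Imputing after the last contact without a report would treat silence as absence and could remove true early events from the window.
- *That a given share of events is affected.* The protocol gives no rate of incomplete dates, so no share can be calculated.
- *That Section 8.5.8 contradicts the rule.* It does say "Missing data will not be imputed", but the specific date rules in 8.5.3.1, 8.5.5.2 and 8.5.9.3 govern over a general sentence.

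**Conclusion.** The point holds for pre-dose events. As written, Section 8.5.3.1 can classify an AE that demonstrably ended before Dose 1 as treatment-emergent, count it in the 7-day and 30-day summaries, and give it a duration of zero or below, as low as −29 days at the edge of the screening period.

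The error is confined to AEs with a partial or wholly missing onset date. Their number is not stated and cannot be derived. Because the imputation ignores treatment arm, the expected consequence is slightly inflated window counts and some added noise in the risk differences, not bias in the comparison. It is a small defect in a stated rule, worth correcting because the rule yields a result that its own inputs contradict.

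**What to change.** Add to Section 8.5.3.1:

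1. The imputed onset date may not be later than the reported or imputed stop date.
2. An AE whose stop date precedes Dose 1, or that was recorded before dosing, is classed as pre-treatment and is not imputed to the dosing day.
3. In all other cases the present conservative rule applies.

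The cost is one or two sentences of text and a minor change to the date-derivation program, made before unblinding. No new data are needed, because stop dates and the pre-dose AE records are already collected.
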